4	Adverse Events.....	14
4.1	Definitions.....	14
4.2	Reporting Procedures	14
4.2.1	Non serious AEs	14
4.2.2	Serious AEs.....	14
4.2.3	Contact details for reporting SAEs	15
5	Assessment and Follow-up	15
6	Statistics and data analysis.....	15
7	Regulatory issues	15
7.1	Ethics approval	15
7.2	Consent and Confidentiality	15
7.3	Data Storage and Retention.....	16
7.4	Indemnity	16

7.5	Sponsor	16
7.6	Funding.....	16
7.7	Audits.....	16
8	Study Management.....	16
8.1	Data Management Committee	17
9	Publication Policy	17
10	References.....	19

Study Summary

TITLE	LumenEye during Covid-19 (LuCID study)
DESIGN	Prospective, observational pilot study, medical device
AIMS	
The main hypothesis is that digital rectoscopy (using the LumenEye system) is safe and acceptable to clinicians including general practitioners and can significantly reduce the burden of endoscopy referral to and within secondary care centres.
 
The secondary objectives are:
 
 1. To assess the safety and acceptability of the LumenEye and CHiP system in primary and secondary care. 2. To establish the clinical utility of the CHiP software system for performing remote telemedicine assessment of the rectum and colon. 3. To provide pilot data for the diagnostic accuracy of the LumenEye system for colitis severity, cancer, rectal polyps and benign disease of the rectum and anus.
OUTCOME MEASURES	
Primary outcome: Both safety and patient and clinical acceptance of the LumenEye device with specialist consultation over the CHiP platform.
 
Secondary outcomes:
 
 1. To establish the clinical utility of the CHiP software system for performing remote telemedicine assessment of the rectum and colon. 2. To provide pilot data for the diagnostic accuracy of the LumenEye system for colitis severity, cancer, rectal polyps and benign disease of the rectum and anus.
POPULATION	Adult patients presenting to either their primary care physician or to secondary care services because of a change in bowel habit, rectal bleeding or assessment for symptoms of established or suspected ulcerative colitis
ELIGIBILITY	
Patients aged 18 and over Patients presenting to primary or secondary care settings With any of:
 
 i) rectal bleeding ii) established ulcerative colitis requiring assessment iii) Positive Faecal occult blood test / Faecal immunochemical test (FIT) or faecal calprotectin iv) any symptom that would warrant referral on the 2WW cancer referral pathway
DURATION	1 year

Reference Diagrams

[figure not shown]

Figure 1: The LumenEye is a CE Marked digital rectoscope

Figure 2: The CHIP software system

1 Introduction

1.1 Background

Rigid sigmoidoscopy (RS) is an established diagnostic procedure used by clinicians worldwide. In the modern context, RS is typically used to make a luminal assessment of the distal gastrointestinal tract; up to 25 centimetres from the anal verge. The typical instrument arrangement consists of four main components: a light source, a rigid tube, a light head (sealed viewing window and fibre optic light connection) and an insufflation bellows. A standard RS also permits the introduction of forceps, needles, and other instruments. Increasingly, RS sets are disposable single use systems, self-lubricating and scope lengths average between 20-25 centimetres with diameters of up to 2 centimetres. The tube is inserted via the anus and has been reported to reach the distal sigmoid flexure in some series.(1)

Anorectal symptoms are a common complaint in both primary and secondary care. These include haematochezia, pruritus ani, proctalgia, anorectal swellings, discharge, change in bowel habit and incontinence. Rigid sigmoidoscopy is therefore typically performed in outpatient clinics in an unprepared bowel by healthcare professionals; particularly: gastroenterologists, general surgeons, primary care physicians and nurses.(2) RS provides clinical value through the early detection of polyps and malignant lesions within the rectum; but it also contributes to therapy and improved patient experience through the detection and management of benign disease.(3) It can be easily deployed for longitudinal assessment of pathology and treatment response and ultimately if used correctly it avoids the requirement for repeat visits for more costly investigations such as flexible sigmoidoscopy. But despite the common use and simplicity of RS as a diagnostic tool, its use is declining as it is replaced by flexible scopes despite its broad range of applications for patient benefit.

We have systematically reviewed this literature as part of this ethical approval process. Of 2,086 citations reviewed, 35 were eligible for analysis which included 27,369 episodes of rigid sigmoidoscopy. RS was used most commonly in secondary care in the assessment of symptomatic patients. It was also used in the screening of asymptomatic patients and in the surveillance and monitoring of patients with anorectal disease. The mean distance reached ranged from 12 to 22.4cm (n=5552). The average time taken was 4 minutes 30 seconds. Adverse events were reported in 11 articles (n= 19,632), the pooled complication rate was 0.01%. Of the three studies to discuss the risk of cross-contamination (n=145 two confirmed a theoretical risk due to bacterial harbouring in reusable components of the device. No patient preparation was used in 8 studies, enemas/suppositories were used in 15 studies and preparation was not reported by 12 studies. General anaesthetic and analgesia were used in children and in patients undergoing another procedure (e.g. laparoscopy, colonoscopy). This is therefore a safe and highly applicable technology.

1.1.1 Colitis assessment

Inflammatory bowel disease (IBD), comprising Crohn's disease (CD) and ulcerative colitis (UC), is a condition in which the gastrointestinal immune system responds inappropriately. IBD is therefore often treated with immunosuppressing medications to control inflammation and prevent 'flares', a worsening of symptoms, which may be unpredictable. While it is known that 0.8% of people in the UK currently have IBD (approximately 524 000 patients), only 44% have been to a clinic in the past 3 years. The greatest risks during Covid-19 relate not only to the infection itself, but also the emergency reorganisation of hospital and general practice services to deal with the pandemic. This has resulted in significant changes to routine IBD services. A combined approach covering both primary and secondary care is therefore required to keep vulnerable patients with IBD out of hospital as much as possible.

Current guidance from the BSG states: “Patients who may require hospitalisation will need to continue to be assessed in a timely manner. Consider the most appropriate location to do this that is away from COVID-19 assessment areas. Daily ‘flare clinics’ (virtual where possible) with limited numbers of patients who are at high risk of imminent hospitalisation should be considered. Where possible, limit visits to hospital and limit the patient journey around the hospital geographically.(4)

1.1.2 Bowel Cancer Screening and 2-week wait referrals

Approximately 1,240,000 new cases of colorectal cancer (CRC) were diagnosed globally in 2008, making it a lethal and highly prevalent disease. There are 16,000 deaths and 41,000 new cases are diagnosed in the UK each year from bowel cancer, affecting 1 in 14 men and 1 in 19 women. 20% of patients present as an emergency and over 50% will have advanced disease, and significantly worse outcome. The number of patients diagnosed with bowel cancer in the UK is set to increase and there is no feasible methodology for prevention. The disease carries a significant cost to the NHS of approximately £1.6 billion annually. A national bowel cancer screening program has thus been developed based on a screening faecal occult blood test. Uptake of the screening programme ranges between 55 to 60% and 2.5% of men and 1.5% of women have an abnormal test. 98% of patients have a colonoscopy as their first investigation. Colonoscopy remains the gold standard for CRC screening despite its associated morbidity and economic cost. Cancer (n=1772) and higher risk adenomas (n=6543) were found in 11.6% and 43% of men and 7.8% and 29% of women investigated, respectively. 71% of cancers were ‘early’ (10% polyp cancer, 32% Dukes A, 30% Dukes B) and 77% were left-sided (29% rectal, 45% sigmoid) with only 14% being right-sided compared with expected figures of 67% and 24% for left and right side from UK cancer registration.(4) However, several studies have demonstrated the efficacy of flexible sigmoidoscopy as a first line screening test, and this is now employed in the UK. The Flexiscope trial reduced the incidence of colorectal cancer by 23% and mortality by 31%. The Incidence of distal colorectal cancer (rectum and sigmoid colon) was reduced by 50%.(5) Therefore, there is a significant need for biomarkers that can support decision making in the selection of the correct definitive follow up investigation(6) and there is an urgent requirement for an office based endoscopy service that can provide the ability to detect rectal cancers during the covid-19 pandemic.

1.1.3 Covid19 and endoscopy services

Despite staff infection rates from endoscopy remaining low during the Covid-19 pandemic (7), staff safety from aerosol transmission remains concern.(8) All but emergency and essential endoscopy has been stopped in response to Covid-19 in the UK, so service provision for the symptomatic and screening populations can be reviewed and reorganised. Data from the National Endoscopy Database shows that the total numbers of endoscopic procedures fell in just 2 weeks in March from 33 000 to 7000 and has fallen further since. When endoscopy services resume, capacity will be significantly reduced due to the additional novel covid-19 cleaning requirements and the significant waiting times that are likely to be present.

1.1.4 LumenEye and CHiP

The intervention: The LumenEye X1 (SurgEase Innovations Ltd, UK) is a CE Marked novel point of care rigid digital endoscope which provides High-Definition views of the rectum up to 20cm from the anal verge. It permits endoscopic biopsy under view (figure 1) and maintains pneumorectum sufficiently with as little as 100ml of air. Air delivery is in a closed system thereby significantly reducing aerosol transmission relative to formal endoscopy. This feature is particularly attractive in the current Covid-19 pandemic. A removable disposable manifold and a chemical clean with Tristel™ Trio is the only requirement for reprocessing

which is more cost-effective than automated washing & sterilisation. All images and videos are displayed on a HD screen, supplied alongside the scope, which can be captured and stored securely on the cloud platform (called CHiP, Figure 2) which allows retrospective review of images and data taken during rectoscopy from any device. The technology permits high quality endoscopy at the bedside and outside of traditional tiers of care which is particularly attractive during the current Corona pandemic. An additional feature of CHiP includes telemedicine functionality with live video sharing of the camera feed; a proctor can be invited over WIFI into a session who can then view the live feed from the scope and offer advice and guidance. The technology can offer cost-effective, immediate tumour visualisation, critical measurement, opportunity for biopsy and virtual diagnostic support.

1.2 Rationale for current study

The LumenEye scope and CHiP platform will be piloted in a number of clinical settings including remote colorectal clinics. The rationale is to perform an initial pilot study to determine the clinical utility of the LumenEye device for use in primary and secondary care settings. The main hypothesis is that digital rectoscopy is safe and acceptable to clinicians including general practitioners and can significantly reduce the burden of endoscopy referral to and within secondary care centres.

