2.1 Recruitment

Patients will be identified for recruitment via two routes:

1. Patients with an established diagnosis of inflammatory bowel disease who have been identified as being 'at risk' by either their secondary care doctor or GP and now require endoscopic assessment for ongoing disease symptoms but are unable to access endoscopy services urgently.
2. Patients presenting directly to their GP practice with symptoms of anorectal disease (e.g. rectal bleeding or pain) or symptoms that would warrant referral to a hospital under a 2WW appointment according to NICE criteria

All patients will be provided with written information about the study and an online website will be created to provide this information. The study aims to recruit 100 patients into the pilot study.

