2.3 Analysis

Clinicians will be asked to provide qualitative feedback data with each use concerning device performance. This will be in the form of a short questionnaire, split into technical performance, views achieved, diagnostic yield, quality of the telemedicine interaction, patient outcome (discharged or referred to formal endoscopy) and adverse events.

Local users of the LumenEye system will undergo nasal swab assessments every 4 weeks for a covid-19 PCR test to ensure staff safety is maintained during the study. If a swab tests positive, the physician will be asked to follow standard PHE advice on isolation, contact tracing and further treatment.

All LumenEye devices will undergo at least one random post-cleaning swab test for Covid-19 to confirm the Tristel Trio cleaning system sufficiently eradicates SARS-COV-2 from the LumenEye. (An analysis of this has been performed outside of the study which confirms the efficacy of the Tristel Trio system against SARS-COV-2).

Patient feedback will be requested through a validated questionnaire..

All clinicians providing advice and guidance via CHiP will be asked to provide data on the quality of the views, the stability of the platform and to provide information on the diagnosis. For flare patients, both clinicians will be asked to report Mayo flare scores based on observed

data. For adenomas, clinicians will be asked to report anatomical location, morphology, and Paris endoscopy assessment scores. All data pertaining to follow up colonoscopy or flexible sigmoidoscopy will be used as a comparator group for a diagnostic sensitivity / specificity analysis.

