2.4 Study Outcome Measures

Primary outcome:

Both safety and patient and clinical acceptance of the LumenEye device with specialist consultation over the CHiP platform.

Secondary outcomes:

1. To establish the clinical utility of the CHiP software system for performing remote telemedicine assessment of the rectum and colon.
2. To provide pilot data for the diagnostic accuracy of the LumenEye system for colitis severity, cancer, rectal polyps and benign disease of the rectum and anus

3 Participant Entry

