3.1 Pre-registration evaluations

All IBD patients requiring urgent flare assessment, patients presenting to their GP with anorectal symptoms, rectal bleeding, change of bowel habit or with a diagnosis that warrants an endoscopy,

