3.2 Inclusion Criteria

- Patients aged 18 and over
- Patients with any of the following:
 - Positive Faecal occult blood test / Faecal immunochemical test (FIT)
 - Positive faecal calprotectin.
 - Established history of polyps and/or adenomas
- 2WW patients referred to a colorectal clinic
- Known IBD patients with flare symptoms
- Patients with a suspected new diagnosis of IBD

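### The main hypothesis claims a significant reduction in endoscopy referral, but the readable plan records referral only after the examination and has nothing to compare it with; the Section 5 time-to-diagnosis aim shares the gap

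*Combined protocol and SAP*

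**What the plan says.** The Study Summary (Aims) and section 1.2 give a main hypothesis in two parts: that the device is safe and acceptable, and that it "can significantly reduce the burden of endoscopy referral to and within secondary care centres".

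The rest of the protocol treats referral as follows.

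- **Design (sections 2 and 2.1).** One prospective observational cohort, with a target of 100 patients. Section 2 calls the analysis confirmatory; section 6 calls the study a feasibility study.
- **Data (section 2.3).** The clinician questionnaire completed with each use includes "patient outcome (discharged or referred to formal endoscopy) and adverse events". This is disposition after the examination.
- **Comparator (section 2.3).** The only one named is follow-up colonoscopy or flexible sigmoidoscopy, which "will be used as a comparator group for a diagnostic sensitivity / specificity analysis".
- **Outcomes (section 2.4).** The primary outcome is "Both safety and patient and clinical acceptance of the LumenEye device with specialist consultation over the CHiP platform". The secondary outcomes are clinical utility of the software and pilot diagnostic accuracy. Section 1.3 lists the same objectives. Referral appears in neither section.
- **Statistics (section 6).** Univariate methods in general terms, with power left to later studies. Referral is not mentioned.
- **Follow-up (section 5).** A further aim is to find out whether the device shortens the time to diagnosis and treatment and betters outcome. No comparison group is described for it.

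**The concern.** A reduction is a statement about two quantities: referral with the device and referral without it. The readable plan yields the first only. When the results are written up, the second has to come from somewhere. The easiest source is the entry criteria: treat every enrolled patient as someone who would have been sent for endoscopy, and count each discharge as a referral averted. The reduction would then be an assumption presented as a finding.

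This matters because the claim stands in the main hypothesis, and section 9 plans summaries for policy makers and commissioners during and after the study. A claim of reduced endoscopy demand is one they could act on.

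**Working it through.** **Step 1. Is there a figure in the plan to reproduce?** No. The target of 100 is given without an effect size, error rate, power or precision, and no baseline referral rate is stated.

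**Step 2. Could anything in the text serve as the rate without the device?**

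- *Route 1 (section 2.1).* These patients have established inflammatory bowel disease and "now require endoscopic assessment for ongoing disease symptoms but are unable to access endoscopy services urgently". Need for endoscopy is an entry condition here, so a baseline near 100% holds by construction.
- *Route 2 (section 2.1).* These patients present to a GP with anorectal symptoms, which do not in themselves imply referral, or with "symptoms that would warrant referral to a hospital under a 2WW appointment according to NICE criteria". The second group implies referral to a hospital, not necessarily to endoscopy.
- *Section 3.1.* Patients "with a diagnosis that warrants an endoscopy" are one alternative among several.
- *Section 3.2.* The criteria include "2WW patients referred to a colorectal clinic". The referral there is to a clinic.
- *Section 1.1.2.* The statement that 98% have colonoscopy as first investigation concerns the screening programme. A positive stool test is only one way into this study, and the figure is not used in any analysis.
- *Section 1.1.3.* The fall from 33 000 to 7000 is a national procedure count, not a referral rate in these patients.

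None of these is a baseline for the cohort. The entry criteria imply a need for endoscopy in some patients, in an unknown share.

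**Step 3. How much does the missing rate matter?** The inputs are n = 100 (section 2.1) and an assumed x = 60 referred after the examination. The exact (Clopper-Pearson) 95% limits are:

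- lower = 2.5% quantile of Beta(x, n − x + 1) = Beta(60, 41) = 49.7%
- upper = 97.5% quantile of Beta(x + 1, n − x) = Beta(61, 40) = 69.7%

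Change = 60% minus the assumed rate without the device. The interval is shifted by the same amount, treating that rate as known.

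| Assumed rate without device | Change in points | 95% CI |
|---|---|---|
| 50% | 60 − 50 = +10 | −0.3 to +19.7 |
| 60% | 60 − 60 = 0 | −10.3 to +9.7 |
| 80% | 60 − 80 = −20 | −30.3 to −10.3 |
| 100% | 60 − 100 = −40 | −50.3 to −30.3 |

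The same data support an increase, no change or a large reduction. Sampling error is about ±10 points; the choice of baseline moves the answer by 50.

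**Step 4. Does a 100% baseline rescue the claim?** No. Under a true rate of exactly 100%, one discharge among 100 patients would be enough to reject it. The test would be passed by any study in which anyone was sent home.

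**The case against.** **It is a pilot, and no listed endpoint promises this test.** True: section 6 says feasibility, and sections 1.3 and 2.4 do not mention referral. That excuses the lack of power. It does not excuse a main hypothesis, printed under Aims in the Summary, that the data cannot address. It does keep the point modest, because no listed endpoint result changes.

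**The word significantly may not be statistical.** The protocol uses it loosely elsewhere (sections 1.1.3 and 1.1.4). This is fair, but reduce is comparative in any sense of the adverb.

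**The paired item adds an endpoint that the sponsor did not choose.** This stands in part. Rewording alone cures the mismatch, so the item is a preference and not a necessity.

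**Stronger readings that the documents do not support.**

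- A reader might infer that the whole study fails for want of a control. It does not: safety, acceptance, software utility and pilot accuracy need no referral comparator.
- A reader might infer the opposite, that everything outside the hypothesis is sound. The time-to-diagnosis aim in section 5 is not.
- A reader might infer that lack of access to endoscopy will by itself produce low referral. Route 1 and section 1.1.3 make that possible, but emergency and essential endoscopy continued, and section 5 follows patients through any warranted investigation.
- A reader might infer that no prior intention is recorded anywhere. Figure 3 and the questionnaire are not in the text, so that cannot be said.

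**Conclusion.** The concern holds for the referral part of the main hypothesis. As far as the text can be read, the plan gives one post-examination proportion and no rate to set against it, so it cannot show a reduction. In the illustration the conclusion runs from a 10-point increase to a 40-point reduction on identical data; the 60 of 100 and the four baseline rates are all assumed. The Section 5 aim on time to diagnosis and treatment has the same defect. The listed primary and secondary objectives are not touched. The conclusion would change only if Figure 3 or the questionnaire contained a pre-examination referral item meant as the comparator.

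**What to change.** 1. **Reword (needed).** In the Summary and section 1.2, replace the reduction claim with a descriptive or estimation aim. Report the post-examination referral proportion with its 95% CI and make no claim of reduction.

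2. **Add a paired item (preferred, so that the study can inform the referral question).** Put one clinician yes/no item in the section 2.3 questionnaire, answered before insertion and repeated in the same words after the examination: on clinical need alone, would this patient be referred for flexible sigmoidoscopy or colonoscopy? Add the change to section 2.4 as a descriptive secondary outcome and to section 6: averted, added and net change, each with a 95% CI, with no formal test. Report it by mutually exclusive entry groups that cover everyone eligible: established inflammatory bowel disease needing endoscopic assessment; GP presenters; and patients already referred to clinic or presenting in secondary care. The two routes in section 2.1 are not enough, because the Summary and section 3.2 admit patients who fit neither. State that where need for endoscopy is an entry condition, the change is close to the discharge rate.

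3. **Align related wording.** Make the Section 5 time-to-diagnosis aim descriptive, and bring confirmatory in section 2 into line with the feasibility status in section 6.

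**Cost.** Items 1 and 3 are text edits. Item 2 adds one question asked twice, an entry-group field and one descriptive table, with no extra patients or visits. Its weakness is that stated intention is an imperfect counterfactual, given by a clinician who knows that the device is about to be used, and precision within entry groups will be low. If only the wording is changed, the study says nothing about whether referral falls.
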